4.3 Participant Withdrawal Criteria

Premature study termination for an individual participant should be taken into consideration under the following circumstances:

- An illness/AE occurs during the study that influences the use, or the assessment of, the investigational medication
- He/she requires a forbidden concomitant medication (see Section 5.8.1)
- Adequate cooperation is not guaranteed

Decisions concerning study termination for individual participants will be made in accordance with the Medical Lead of the study and the Sponsor.

Premature study termination for an individual participant is mandatory under the following circumstances:

- Lack of efficacy and progressive disease (e.g. T levels >2 ng/mL)
- Lost to follow-up (the participant did not show up for the examination and the study personnel were unable to contact the participant)
- Death of the participant

The study must be terminated for an individual participant if the participant withdraws his/her consent or it is, in the investigator's opinion, necessary from a medical point of view (e.g. allergic reactions to the study medication).

If possible, a complete final examination, as planned for the visit that takes place on Day 168, should be carried out and documented on the corresponding pages of the electronic case report form (eCRF) for all participants who stop taking part in the study. If possible, the participant will also be asked to return to the site for a safety follow-up visit 28 days after the last administration of teverelix TFA.

Although participants may withdraw from the study at any time without giving any reasons, efforts should be made to find out the cause and document it.

For follow-up of participants' withdrawal because of an AE please see Section 6.3.7.3.

ANT-1111-02, Teverelix TFA in Prostate Cancer

FINAL Version 5.0, 31 May 2022

Page 37 of 84

Participants who terminate the study prematurely will not be replaced.

For criteria concerning the termination of the whole study please refer to Section 7.3.2.

5 Study Treatments

The IMP to be tested in this study is teverelix TFA, which is administered on Day 0 as a loading dose, followed by a maintenance dose as per the schedule below.

5.1 Treatments Administered

Participants will receive different doses depending on whether they join Group 1 or Group 2. The study will enrol participants into Group 1 first.

On Day 0, participants will receive a single loading dose consisting of 2 injections, each of which will contain 120 mg of teverelix TFA (Group 1). The first injection will be administered as an IM injection and the second as an SC injection (Stage 1). After Stage 1, participants will receive a maintenance dose, which in Group 1 will consist of a single 120 mg SC injection administered every 42 days, and in Group 2, will consist of a single 180 mg SC injection administered every 42 days (see Table 1).

If treatment of Group 1 has been terminated early due to a low therapeutic response rate, recruitment into Group 2 will start.

The total treatment period will be up to 168 days (24 weeks) in the core study, or until treatment ceases to be effective (serum T >2 ng/mL).

Participants withdrawn early from the study will be asked to return to the study site 28 days after the last dosing for a safety follow-up visit.

Depending on the safety and efficacy of the study drug observed during the core study, participants who complete the core study and who maintain serum T levels (local laboratory) ≤2 ng/mL at the end of the core study (at the Day 168 visit) may be offered the opportunity to continue in an extension study, during which the maintenance treatment will be continued up to D336. The decision to extend the treatment period for eligible subjects will be made when 5 or more subjects have reached D28 with D21 local laboratory T levels ≤ 2 ng/mL.

5.2 **Identity of Investigational Product(s)**

[figure not shown]
Table 2 presents the details of the IMP.

Table 2: Investigational Medicinal Product Details

Active Ingredient	Teverelix TFA
Brand name	-
Dosage form	Powder presented in glass vials (powder weight is 250 mg net weight with 200 mg base weight)
Strength	120 mg (Group 1) and 180 mg (Group 2) injection
Frequency	Every 6 weeks (Groups 1 and 2)
Route of administration	Loading dose: IM injection followed by SC injection Maintenance dose: SC injections
Supplied by	Antev Ltd.

IM=intramuscular; IMP=investigational medicinal product; SC=subcutaneous

ANT-1111-02, Teverelix TFA in Prostate Cancer FINAL Version 5.0, 31 May 2022

Page 38 of 84

5.3

Method of Assigning Participants to Treatment Groups

All enrolled participants will be identifiable throughout the study. The investigator will maintain a personal list of participant numbers and participant names to enable records to be found at a later date.

Upon enrolment each participant receives a 5-digit screening number, which is sufficient for unambiguous identification:

Digits 1 and 2: Study centre (11, 12, 13, etc.)

Digits 3, 4 and 5: Individual participant number within the centre (consecutively in

the order of enrolment within the centre: 001, 002, etc.)

Enrolled participants who drop out of the study before their baseline visit will retain their screening number.

On completion of the screening phase, the participant's eligibility will be confirmed. Eligible participants will receive treatment on Day 0. All participants will receive the same dose per treatment group (Group 1 or Group 2) of teverelix TFA as defined in Section 5.1. Medication will be dispensed in numerical order, starting with the smallest number available in the centre.

5.4 **Selection of Doses in the Study**

The goal of this study is the selection of an optimal treatment regime, which allows achievement of the highest level of efficacy with an acceptable safety profile and optimal convenience for patients and physicians. For this reason, 2 treatment regimens will be evaluated.

The treatment regimen for Group 1 comprises a dose of 120 mg administered SC and IM as a loading dose and SC as a maintenance dose every 6 weeks. For Group 2, the dose will be 180 mg administered SC and IM as a loading dose and SC as a maintenance dose every 6 weeks. The 180 mg dosage has been administered in 4 Phase 1 studies conducted in healthy male volunteers and 2 Phase 2 studies conducted in participants with APC. No severe or serious AEs were noted in these studies. The dosing regimen and treatment period will be according to the details described in Section 5.1.

5.5 **Selection and Timing of Dose for Each Participant**

Participants will receive different doses depending on whether they join Group 1 or Group 2. The study will enrol participants into Group 1 first.

On Day 0 participants will receive a single loading dose consisting of 2 injections, each of which will contain 120 mg of teverelix TFA (Group 1) or 180 mg (Group 2). The first injection will be administered as an IM injection and the other as an SC injection (Stage 1).

After Stage 1, participants in Group 1 will receive a maintenance dose, which will consist of a single 120 mg SC injection administered every 42 days.

[figure not shown]
If the serum T value (measured by the local laboratory) at the Day 35 visit is >2 ng/mL, the participant will be withdrawn from the study.

If 3 or more participants have a total T (local laboratory) value of >2 ng/mL at Day 21 or at any subsequent study visit, the dosing regimen will have failed to meet its 90% efficacy target and, if applicable, further enrolment into Group 1 will cease.

If treatment of Group 1 has been terminated early due to a low therapeutic response rate, recruitment of participants into Group 2 will start.

After Stage 1, participants in Group 2 will receive a maintenance dose, which will consist of a single 180 mg SC injection administered every 42 days.

Page 39 of 84

If the serum T value (measured by the local laboratory) at the Day 21 visit is >2 ng/mL, the participant will be withdrawn from the study.

Participants will have their serum T measured by the local laboratory 1 week prior to each maintenance dose during Stage 2 of the study. If, at any point the local laboratory serum T result is >2 ng/mL the participant will be withdrawn from the study. Local laboratory serum T values ≤ 2 ng/mL allow the subjects to continue in the study.

Table 3 describes the decision-making process for doses participants will receive based on the results of the locally analysed T level from 7 days prior to the scheduled dosing visit.

Table 3: Decision-making in Relation to Serum Testosterone Levels

[T] (ng/mL)	Action Taken	Dose Administered
≤2	Continue in Stage 2	Group 1: Maintenance dose 120 mg
		SC teverelix TFA
		Group 2: Maintenance dose 180 mg
		SC teverelix TFA
>2	Withdrawal from study, safety	None
	follow-up visit	

SC=subcutaneous; T=testosterone; TFA=Trifluoroacetate

Depending on the level of T prior to dosing, a decision will be made regarding whether to continue the participant in the study, request a re-test 7 days prior to the next scheduled dosing visit, or initiate early study withdrawal. If T levels are ≥ 2 ng/mL, the participant will be withdrawn from the study.

In the event that a participant of Group 1 will be continued during Stage 2, each dose will be administered according to Table 4: Testosterone Testing in Groups 1 and 2 every 6 weeks.

Table 4: Testosterone Testing in Groups 1 and 2

Local [T] Testing	Teverelix TFA Dose
DAY 21 [T]	DAY 28: No teverelix TFA dose
DAY 35 [T]	DAY 42: Maintenance dose 120 or 180 mg SC
DAY 77 [T]	DAY 84: Maintenance dose 120 or 180 mg SC
DAY 119 [T]	DAY 126: Maintenance dose 120 or 180 mg SC
DAY 161 [T]	DAY 168: Maintenance dose 120 or 180 mg SC
*DAY 203 [T]	No dose
*DAY 210 [T]	No dose
*DAY 217 [T]	No dose
*DAY 224 [T]	No dose
*DAY 231 [T]	No dose
*DAY 238 [T]	No dose
*DAY 245 [T]	No dose
*DAY 252 [T]	No dose

SC=subcutaneous; T=testosterone

^{*}Group 2 subjects with Stage 3 only

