SC=subcutaneous; T=testosterone; TFA=Trifluoroacetate For participants in Group 2, the following actions will be taken at the Day 28 visit based on the results of the locally analysed T level determined from the Day 21 visit:

[T] (ng/mL)	Action Taken	Dose Administered
≤2	Continue with Stage 2 of Group 2	No dose on Day 28. Maintenance dose of 180 mg SC teverelix TFA every 42 days
>2	Withdraw from study; safety follow-up visit on Day 28	None

SC=subcutaneous; T=testosterone; TFA=Trifluoroacetate

Day 35 Visit

On Day 35, local testing of T levels will be performed to guide decision making at the Day 42 visit. PK, total T, LH, FSH and PSA (total and high-sensitivity [hs]) samples will also be collected for central laboratory analysis.

Stage 2 Visits in Groups 1 and 2

Day 28 Visit

Stage 2 will start at the Day 28 visit. However, participants will receive their first maintenance dose at the Day 42 visit and participants will visit the clinic at Day 35 to provide a blood sample for local laboratory testing of T levels.

Blood samples for PK and PD analyses (T, LH, FSH, PSA), and fasted (≥8 hours) safety laboratory testing will be collected. Samples will also be collected for urine analysis. AE assessment, physical examination, triplicate 12-lead ECG and assessment of vital signs (including sitting blood pressure and heart rate) will be performed.

If, in the opinion of the investigator, no safety concerns exist, participants will be discharged from the centre.

Visits at Day 42, Day 84, Day 126, and Day 168

On Day 42 the first maintenance dose will be administered.

Before administration of the maintenance dose, blood samples for PK and PD analyses as well as fasted (≥8 hours) safety laboratory testing will be collected. Samples will also be collected for urine analysis. Pre-dose AE assessment (including ISR), physical examination, triplicate 12-lead ECG and assessment of vital signs (including sitting blood pressure and heart rate) will be performed.

Participants will attend the clinic 1 week before each maintenance dose is given (i.e. at Days 35, 77, 119 and 161) to provide a blood sample for local laboratory assessment of T levels. At the Day 35 visit (only) PK, total T, LH, FSH and PSA (total and hs) samples will also be collected for central laboratory analysis. Based on the results of the local analysis of T level from 7 days prior to the scheduled visit, participants will receive:

[T] (ng/mL)	Action Taken	Dose Administered

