1	120 mg IM +120 mg SC	120 mg SC	6 weekly
2	180 mg IM +180 mg SC	180 mg SC	6 weekly

IM=intramuscular; SC=subcutaneous

Initially enrolment will open for Group 1 only. If, after Day 28, a participant's serum T value (as tested by the local laboratory on Day 21) is >2 ng/mL, the participant will be withdrawn from the study.

Enrolment will continue for Group 1 until 20 participants have completed the Day 28 visit with no more than 2 participants being classified as a treatment failure. Treatment failure is defined as having a T level >2 ng/mL at Day 28 (as tested by the local laboratory on Day 21) or requiring to be withdrawn at any later timepoint during the study.

If 3 or more participants fail treatment in Group 1 then further enrolment into that group will stop due to statistical confidence that a 90% responder rate cannot be achieved with that dosing regimen. All future participants will be enrolled into Group 2.

If in Group 2 at Day 28, a participant's serum T value (as tested by the local laboratory on Day 21) is >2 ng/mL, the participant will be withdrawn from the study.

If 7 or more participants fail in Group 2 then all further enrolment will be stopped and the study will be terminated.

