4.2 Participant Exclusion Criteria

If any of the following criteria apply, the participant MUST NOT be admitted to the study. The participant:

1. Has abnormal screening and/or baseline laboratory values that suggest a clinically significant underlying disease, or the following laboratory values:

- a. Liver function test (aspartate aminotransferase [ASAT/SGOT], alanine aminotransferase [ALAT/SGPT]), or total bilirubin exceeding twice the upper limit of the normal (ULN) range
- b. Creatinine twice the ULN range
- c. Uncontrolled diabetes (HbA1c >7.5%) or previously undiagnosed diabetes mellitus with HbA1c >6.5%
- 2. Has any contraindication to the use of teverelix TFA
- 3. Has a life expectancy of less than 1 year
- 4. Has T levels <2.0 ng/mL at screening
- 5. Has a medical history of bilateral orchidectomy
- 6. Using any of the following prohibited treatments:
 - a. Within 25 weeks prior to screening: dutasteride
 - b. Within 12 weeks prior to screening: finasteride
 - c. Current use of any of the following:
 - i. Anti-androgen therapy, including T replacement therapy and 5α -reductase inhibitor treatment etc. (Spironolactone is a permitted concomitant treatment)
 - ii. Any other medication or herbal product that may affect hormone levels and might, therefore, confound interpretation of the study results (e.g. St. John's wort)
- 7. Has neurological disease, psychiatric disease, drug or alcohol abuse, which could interfere with the participant's proper compliance
- 8. Has a history of myocardial infarction, unstable symptomatic ischaemic heart disease, any ongoing cardiac arrhythmias of grade >2 (chronic stable atrial fibrillation on stable anticoagulant therapy is allowed), thromboembolic events (e.g. deep vein thrombosis, pulmonary embolism, or symptomatic cerebrovascular events), or any other significant cardiac condition (e.g. pericardial effusion, restrictive cardiomyopathy) within 6 months before screening
- 9. Has congenital long QT syndrome or ECG abnormalities at screening of:
 - a. Q-wave infarction, unless identified ≥6 months before screening
 - b. Fridericia corrected QT interval (QTcF interval) >480 msec. If QTcF is prolonged in a participant with a pacemaker, the participant may be enrolled in the study upon discussion with the project clinician

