**Table 1 Dosing Regimens under Evaluation**

Group	Loading Dose	Maintenance Dose	Dosing Interval
1	120 mg IM +120 mg SC	120 mg SC	6 weekly
2	180 mg IM +180 mg SC	180 mg SC	6 weekly

IM= intramuscular; SC= subcutaneous

Initially enrolment will open for Group 1 only. If, after Day 28, a participant's serum T value (as tested by the local laboratory on Day 21) is  $>2$  ng/mL, the participant will be withdrawn from the study.

Enrolment will continue for Group 1 until 20 participants have completed the Day 28 visit with no more than 2 participants being classified as a treatment failure. Treatment failure is defined as having a T level  $>2$  ng/mL at Day 28 (as tested by the local laboratory on Day 21) or requiring to be withdrawn at any later timepoint during the study.

If 3 or more participants fail treatment in Group 1 then further enrolment into that group will stop due to statistical confidence that a 90% responder rate cannot be achieved with that dosing regimen. All future participants will be enrolled into Group 2.

If in Group 2 at Day 28, a participant's serum T value (as tested by the local laboratory on Day 21) is  $>2$  ng/mL, the participant will be withdrawn from the study.

If 7 or more participants fail in Group 2 then all further enrolment will be stopped, and the study will be terminated.

Document:

C:\ProgramData\activePDF\Temp\DocConverter\API\Input\\$651f4dc0b253\$FE3041C5883446E892B20AB6D3F0E1BD.docx

Author: [name]

Version and Date: Version 1.0, 21 Apr 2023

Page 12 of 66

Table 2 presents the testosterone testing schedule in Groups 1 and 2.

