#### **4.1.2.1 Local Lab T Level**

Local lab serum T level (ng/mL) and number of subjects with local lab serum T <2 ng/mL will be measured at Screening, Visit 11/Day 21 and 7 days prior to each dosing visit. For comparison, the number of subjects with local lab serum T  $\geq$ 2 ng/mL will also be recorded. See Table 8 below.

Local laboratory data will not be reported.

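### Protocol 5.5 both doses and withdraws a man whose pre-dose local testosterone is exactly 2 ng/mL; SAP 4.1.2.1 cuts local testosterone on the wrong side of 2 after baseline and leaves it unreported

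*Protocol*

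**What the plan says.** Protocol 5.5 sets the dosing decision from local T drawn 7 days before each maintenance dose. Above Table 3: "Local laboratory serum T values ≤ 2 ng/mL allow the subjects to continue in the study". Table 3 repeats this, with a dose at ≤2 and withdrawal at >2. The paragraph directly below Table 3, which concerns T before dosing, says: "If T levels are ≥ 2 ng/mL, the participant will be withdrawn from the study".

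The Group 1 stopping rule in the same section counts only values above 2: "If 3 or more participants have a total T (local laboratory) value of >2 ng/mL at Day 21 or at any subsequent study visit". Protocol 3.1 and 8.1.2 and SAP 2.2.1 define treatment failure, in the Group 1 enrolment paragraph, as T above 2 at Day 28 "or requiring to be withdrawn at any later timepoint during the study". For Group 2 the SAP says: "If 7 or more participants fail in Group 2 then all further enrolment will be stopped, and the study will be terminated".

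SAP 4.1.2.1 gives a count below 2: "subjects with local lab serum T <2 ng/mL will be measured at Screening, Visit 11/Day 21 and 7 days prior to each dosing visit", with the count at ≥2 recorded alongside for comparison. It then says that local results are not reported. Protocol 8.1.8 and the synopsis (Statistical Methods) commit to listing all data by participant. SAP 7.1 names the changes from the protocol: the relabelled time-to-event analyses, the FDA-recommended Kaplan-Meier analysis, and added PSA, FSH and LH analyses. Local T is not among them.

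**The concern.** Local T is the operational measurement of this trial. It decides whether a man gets his next dose, and through withdrawals it can feed the rule that ends the study. A site that follows the sentence below Table 3 would withdraw a man whom Table 3 tells it to dose. The SAP then places that man, correctly dosed under Table 3, on the same side of the cut as the failures. If local T is also missing from the report, a reader sees that men were withdrawn but not the values that led to it.

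**Working it through.** The plan attaches no figure to this point, so there is none to reproduce. The check applies each written rule to values around 2 ng/mL and then counts the draws concerned.

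**1. The rules at the boundary**

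| Local T (ng/mL) | Text above Table 3, and Table 3 | Sentence below Table 3 | SAP 4.1.2.1 category |
|---|---|---|---|
| 1.99 | continue, dose | continue | <2 |
| 2.00 | continue, dose | withdraw | ≥2 |
| 2.01 | withdraw | withdraw | ≥2 |

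The protocol contradicts itself only at 2.00. At that value the SAP category also departs from Table 3.

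**2. Which symbol is wrong**

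The synopsis text and action tables, protocol 3.1, 4.3, 5.1 and 8.1.2, the other sentences of 5.5, and SAP 2.2.1 all withdraw or count failure at >2, or continue at ≤2, or both. No other dosing or withdrawal rule uses ≥2. The intended rule is therefore >2.

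**3. The SAP cut**

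Splitting at <2 and ≥2 suits Screening, where exclusion criterion 4 reads: "Has T levels <2.0 ng/mL at screening". It does not suit Day 21 or the pre-dose visits, where failure means >2.

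**4. Which draws are concerned**

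- Protocol Table 4 gives pre-dose draws at Days 35, 77, 119 and 161, which is 4 per man. With 60 Group 2 men the maximum is 60 × 4 = 240 results.
- Adding Day 21 gives 5 draws that can lead to withdrawal: 60 × 5 = 300 results.
- Day 21 has same-day central T. Among the pre-dose draws only Day 35 does: "At the Day 35 visit (only) PK, total T, LH, FSH and PSA (total and hs) samples will also be collected for central laboratory analysis". Days 77, 119 and 161 are local only (protocol Table 9, SAP Table 7): 60 × 3 = 180 results.
- Protocol Table 14 and SAP Tables 8 and 18 footnote Day 35 as Group 1 only, whereas the synopsis and protocol Tables 4 and 9 schedule it for both groups. If the footnote is right, Group 2 has 3 pre-dose draws (60 × 3 = 180) and 4 decision draws (60 × 4 = 240).
- The local-only share is then 180/300 = 60%, or 180/240 = 75% under the footnote. These counts are maxima, because they assume that all 60 men stay to Day 161.

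The next planned central samples after the local-only draws are at Days 84, 126 and 168. For a man withdrawn earlier there may be a final examination, which protocol 4.3 asks for only where possible. None of these is the value that decided the withdrawal.

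**5. What cannot be computed**

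The effect on the Group 2 limit of 7 would need the frequency of results of exactly 2, the rounding used by the local laboratories, and the share of such men who would not exceed 2 at a later draw anyway. The documents give none of these.

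**The case against.** The strongest reply is that this is a one-symbol slip with an obvious correction. Table 3 stands directly above the sentence and is explicit, and the rest of the protocol agrees with it. That is right about the intent, and it is why the point is minor. It does not remove the need to correct a threshold that sites act on.

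A second reply concerns reporting. The SAP may mean only that local T gets no summary table. The output shells could still contain a listing, and they are not among the documents. Protocol 8.1.9 asks that deviations be defined in the SAP, and 4.1.2.1 does state the omission openly; SAP 7.1 is headed as changes to analyses, so whether a dropped listing belongs there is arguable. This stands in part, and it lowers confidence. But the SAP sentence carries no such limit, no local T listing is promised elsewhere in the SAP, and no reason is given.

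A third reply is that SAP 6.1 reports the primary reason for withdrawal, so failures can partly be recovered. That is so, but the reason is not the value. Likewise, the <2 and ≥2 split does no harm while local T goes unreported; it would misclassify a result of 2 as soon as it were used.

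A reader might infer that the conflict materially raises the chance of stopping Group 2. The documents do not support that. Any such figure would rest on an invented frequency of results at exactly 2, and would count as an additional failure a man who might later exceed 2 under the undisputed rule. The link to the limit of 7 is itself an inference, because the definition that counts later withdrawals is written in the Group 1 paragraph, while the Group 2 rule does not define failing.

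**Conclusion.** The threshold conflict is real and confined to pre-dose local results of exactly 2 ng/mL. Their number is unknown and may be zero. A man withdrawn on such a result would count towards the Group 2 limit if the failure definition in protocol 3.1 and 8.1.2 and SAP 2.2.1 carries over from Group 1. Group 1's closing decision is already past, since Group 2 men were enrolled under protocol version 4.0.

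A reader might also infer that the primary result is affected. It is defined on central T below 0.5 ng/mL at Day 28, so local T does not enter it except through withdrawal.

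The reporting gap does not depend on results of exactly 2. As written, the SAP leaves out the values that drive withdrawal, against the protocol's listing commitment and with no entry in SAP 7.1. Three of the five draws that can lead to withdrawal (three of four if Day 35 does not apply to Group 2) have no same-day central T to stand in for them.

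Severity is minor. Confidence is high on the threshold conflict and moderate on the reporting point.

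**What to change.** - **Protocol 5.5, below Table 3:** change ≥2 to >2. This is one symbol, but protocol 10.2 requires a formal amendment for any change, so it is best carried with the next one.
- **SAP 4.1.2.1, cut:** keep <2 and ≥2 at Screening, and use ≤2 and >2 at Day 21 and each pre-dose visit.
- **SAP 4.1.2.1, reporting:** provide a participant listing of local T. If it is to be left out, say so in SAP 7.1 with the reason. If only summary tables were meant to be excluded, say that instead.
- **Optional:** counts by group and visit on each side of the cut, and cumulative failures. The protocol's data-listing commitment does not extend to these.

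The listing uses data already collected. Stating in protocol 3.1 and 8.1.2 and SAP 2.2.1 whether the failure definition applies to Group 2 would settle the remaining ambiguity in one clause.
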